Regardless of indication, the success of colonoscopy is linked closely to the adequacy of preprocedure bowel cleansing. Quality of bowel preparation is based on ability to visualize the mucosa after retained stool and fluid have been suctioned away. The endoscopist should document the quality of the bowel preparation in each colonoscopy. [5] Unfortunately, up to 20%–25% of all colonoscopies are reported to have an inadequate bowel preparation. The reasons for this range from patient-related variables such as compliance with preparation instructions and a variety of medical conditions that make bowel cleansing more difficult to unit-specific factors (eg, extended wait times after scheduling of colonoscopy). Adverse consequences of ineffective bowel preparation include lower adenoma detection rates, longer procedural time, lower cecal intubation rates, increased electrocautery risk, and shorter intervals between examinations. [4]

Traditionally, patients are instructed to ingest only clear liquids the day before colonoscopy. Recent randomized trials report that a liberalized diet the day before colonoscopy is associated with better tolerance of the preparation and comparable or better bowel cleansing.

A less restrictive low residue diet may improve colonoscopy bowel preparation quality compared with a clear liquid diet, according to interim randomized controlled trial data presented at Digestive Disease Week in May, 2016. The mean Boston Bowel Preparation Score was 7.98 with the low residue diet vs. 7.54 with the clear liquid diet, which was not statistically significant; however, the low residue diet group had significantly more adequate bowel preparations (91.3% vs. 75.7%; P = .05). The study also showed the low residue diet improved patient satisfaction and tolerability, and could help to increase patient participation in colorectal cancer screening programs. [7]

However, there are nopublished local guidelines on the use of low residue diet for bowel preparation. There is also insufficient evidence to recommend specific dietary regimens for special populations such as the elderly , diabetes, chronic kidney disease, chronic liver disease patients.

Objectives

a. General:

To determine the efficacy of low residue diet for colonoscopy bowel preparation in the special populations (elderly, diabetes mellitus, chronic kidney disase, chronic liver disease) versus clear liquid diet using the Boston Bowel Preparation Scale (BBPS).

b. Specific

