improve patients' compliance and experience and may potentially improve their future participation in colorectal cancer prevention programs without compromising examination quality. We want to test the hypothesis that the use of a low residue diet the day prior to colonoscopy was not inferior to consuming clear fluids alone in patients undergoing colonoscopy. It is the researcher's hope that a low residue diet may help alleviate patient concerns with bowel preparation experience and potentially improve patient participation in colorectal cancer prevention programs without compromising examination quality. It is also the researchers hope to determine the efficacy of low residue diet in special populations (ie,diabetes mellitus, CKD,CLD and elderly)

Methodology

Study Area

The study will be conducted at the out-patient department (OPD), wards and endoscopy unit of Veterans Memorial Medical Center until target population is reached

Study Design

This study is a prospective single-blinded, randomized controlled non-inferiority trial. All eligible patients will be included in the study. Patients will be randomized using block randomization. There are no benefits or compensations that will be provided for the patients in this study.

Intervention

All eligible patients subjected for screening colonoscopy at the OPD and wards will be included in the study. Medical risk evaluation, if necessary, will be done even prior to enrollment. As in everyprocedure, the risks and complications of colonoscopy will be highly explained. Outmost care and safety during the procedure will be assured to the patients as this will all be done with the assistance of service consultants.

All the procedures will be done by the GI consultants and fellows in-training with the assistance of service consultant for the day (see Appendix A for the list of service consultants per day). The patients will be randomized into two groups: those following the low residue diet regimen, and those on the clear liquid diet regimen. Each patient will receive oral and written instructions regarding the diet and cathartics to be ingested prior to scheduled colonoscopy.

Those patients randomized to the clear liquid regimen will be asked to take only clear liquids the entire day before their procedure. The low residue diet regimen group will consume the prescribed low residue diet until 6 pm the day before the procedure or 12 hours prior to scheduled colonoscopy.

Bowel cleansing regimen

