[figure not shown]
All patients will be instructed to ingest the standard operating procedure (SOP) bowel cleansing agent of VMMC. Patients whose colonoscopy was scheduled at 8 AM will be instructed to take lactulose 60cc followed by 4-5 glasses of water at 1pm, 3pm and 5pm the day before the procedure. They will also be instructed to take bisacodyl 5mg/tab, 2 tablets followed by 4-5 glasses of water at 7pm. Those patients schedule after 8am will follow the same regimen. They will be instructed to take the lactulose and bisacodyl 15 hours and 12 hours respectively prior to colonoscopy.

[figure not shown]
Outcomes

[figure not shown]
The primary outcome is the efficacy or adequacy of bowel preparation. It will be measured by the Boston Bowel Preparation Scale (BBPS), which is a validated and reliable scale. Secondary outcomes such as patient's tolerability of the regimen will be assessed by inquiring on the occurrence of gastrointestinal symptoms related to the dietary regimen, i.e, nausea, vomiting, bloatedness, abdominal cramps/discomfort. Other outcomes such as cecal intubation rate, polyp detection rate and insertion/withdrawal time will also be measured.

The efficacy of bowel preparation will be assessed by three gastroenterology consultants blinded to the bowel preparation. An adequate bowel preparation will be given a BBPS score of ≥ 6 . The secondary outcomes will also be assessed on the day of the procedure. Before colonoscopy patients will be asked to complete a questionnaire to assess their tolerability, hunger score and satisfaction with the dietary regimen. A subgroup analysis to assess the efficacy of bowel preparation on special population will also be conducted.

Study Process

Study Population

Inclusion Criteria:

 All adults≥18 years of age scheduled for colonoscopy at VMMC and willing to sign informed consent were eligible for ourstudy

Exclusion Criteria:

- 1. Patients with bowel obstruction and/or bowel perforation
- 2. Presence of a colostomy and/or history of a partial colon resection
- 3. Active gastrointestinal bleeding
- 4. Pregnancy
- 5. Inflammatory bowel disease
- 6. Diverticulitis

Sample Size:

At 95% confidence interval and 80% power of test, the minimum required sample size is 75 patients per group. This is also based on the previous proportion of adequate bowel preparation of 91% among low residue diet while 76% for clear liquid diet.

Statistical Analysis:

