Baseline characteristics of the patients will be described as mean and standard deviation among continuous variables while percentage will be utilized for categorical data. In comparing the two groups, t-test will be used to compare means such as BBPSscore, while chi square test will be utilized for categorical variables such as proportion of adequate bowel preparation. All significant test will be done at 5 % level. A non inferiority margin of 0.05 was set. Medcalc statistical calculator will be utilized to carry out statistical computations.

Results

Patients Demographics

A total of 75 patientseach from low residue diet and clear liquid diet group were included in this study whose average age is 67.9 and 64.9 respectively (p=.0515). (Table 1). It also showed that around 82.7% of the patients in low residue are elderly, which is not significantly different from the resulting proportion of elderly patients in clear liquid diet group (72%). (Table 1) Moreover, both group is composed mostly of male (61% vs 75%, Low Residue vs Clear liquid), while proportion of occurrence of diabetes mellitus, chronic kidney disease and chronic liver disease is also not significantly different for the two groups.(Table 1). There were also no differences in terms of cecal intubation rate, withdrawal time, out patients and in patient's number.(Table 1).

Table 1. Patient Baseline Demographic Information

Profile	Low Residue Diet (n=75)	Clear Liquid Diet (n=75)	p value
Age (years), mean±sd	67.9 ± 9.5	64.9 ± 9.0	0.0515 ^{ns}
Elderly (>60), n,%	62 (82.7)	54 (72.0)	0.1200 ^{ns}
Sex, n,%			
Male	46 (61.3)	56 (74.7)	0.0811 ns

Female	29 (38.7)	19 (25.3)	
Comorbidities, n,%			
Diabetes Mellitus	32 (42.7)	29 (38.7)	0.6192 ns
Chronic Kidney Disease	11 (14.7)	6 (8.0)	0.1993 ns
Chronic Liver Disease	5 (6.7)	5 (6.7)	1.0000 ns
Others			
Cecal intubation rate	75 (100)	75(100)	1.0
Withrawal time	8.6±2.2	8.95±2.5	0.3642
In patients	44(58.7)	39(52)	0.4131
Out patients	31(41.3)	36(48)	

Adequacy of Bowel Preparation

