The mean Boston Bowel Preparation Score was 7.00 ± 1.12 with the low residue diet(LRD) vs. 6.90 ± 1.12 with the clear liquid diet(CLD), which was not statistically significant. LRD bowel preparation quality was non inferior to CLD bowel preparation quality (LRD 7.0 vs. CLD 6.9) (Table 2). Bowel preparation was considered adequate if the BBPS score was equal or higher than 6. Both colon preparation regimens were adequate for colon cleansing (92% vs 90.7%). No significant differences were observed between the treatment groups(92% vs 90.7%, p=0.7724). Likewise, same conclusion can be derived from patients with Diabetes, Chronic Kidney Disease, chronic liver disease, and among elderly patients.(Table 2b-2e).

Table 2a. Boston Bowel Preparation Scale (BBPS) Scores

Outcome	Low Residue Diet (n=75) Clear Liquid Diet (n=75)		p value
BBPS Score, mean±sd	7.00 ± 1.12	6.90 ± 1.12	0.6095 ^{ns}
BBPS Score≥6, n, %	69 (92.0)	68 (90.7)	0.770.4ns
BBPS Score<6, n,%	6 (8.0)	7 (9.3)	0.7724 ^{ns}

Table 2b. Boston Bowel Preparation Scale (BBPS) Scores for Diabetes

Outcome	Low Residue Diet (n=32)	Clear Liquid Diet (n=29)	p value
BBPS Score, mean±sd	6.89 ± 1.17	7.01 ± 1.14	0.6722 ^{ns}
BBPS Score≥6, n, %	27 (84.4)	27 (93.1)	0.2894 ^{ns}

BBPS Score<6, n,%	5 (15.6)	2 (6.9)	
-------------------	----------	---------	--

Table 2c. Boston Bowel Preparation Scale (BBPS) Scores for CKD

Outcome	Low Residue Diet (n=11) Clear Liquid Diet (n=6)		p value
BBPS Score, mean±sd	6.79 ± 1.21	7.11 ± 1.19	0.6034 ^{ns}
BBPS Score≥6, n, %	10 (90.9)	6 (100.0)	1 00000
BBPS Score<6, n,%	1 (9.1)	0 (0.0)	1.000 ^{ns}

Table 2d. Boston Bowel Preparation Scale (BBPS) Scores for CLD

Outcome	Low Residue Diet (n=5)	Clear Liquid Diet (n=5)	p value
BBPS Score, mean±sd	7.33 ± 1.45	6.47 ± 1.50	0.3802 ^{ns}
BBPS Score≥6, n, %	4 (80.0)	4 (80.0)	1 00000
BPPS Score<6, n,%	1 (20.0)	1 (20.0)	1.000 ^{ns}

Table 2eBoston Bowel Preparation Scale (BBPS) Scores for Elderly (Age≥60)

Outcome	Low Residue Diet (n=62) Clear Liquid Diet (n=54)		p value
BBPS Score, mean±sd	7.06 ± 1.15	6.90 ± 1.09	0.4333 ^{ns}
BBPS Score≥6, n, %	57 (91.9)	49 (90.7)	0.010008
BBPS Score<6, n,%	5 (8.1)	5 (9.3)	0.8199 ^{ns}

Patient Tolerance and Satisfaction

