From a patient standpoint, bowel preparation remains the biggest deterrent to an elective colonoscopy examination. Bowel preparations are generally poorly tolerated, which results in an important impediment to colorectal cancer screening and surveillance. Tolerability, often measured in clinical trials with "willingness to retake the preparation" or with respect to taste of the purgative solution, involves other factors that may lead to negative patient assessment. These include various dietary modifications or restrictions and important adjustments in work or social schedule that may affect the pre-procedural quality of life and directly influence adherence.

Overall, patient's tolerability and satisfaction were better in the LRD group than the CLD group. The present study showed that the proportion of patients having abdominal pain/cramping/discomfort and bloatedness are significantly lower in LRD group compared to CLD group. In addition, the proportion of patients in the LRD group was less hungry before colonoscopy as compared to CLD group. Our study also showed a higher proportion of patients in the LRD group rated the procedure easy and fair compared to CLD group. These results were parallel to other studies.

However, in our subgroup analysis, no difference was found among diabetics, chronic kidney disease and chronic liver disease patients when the two groups were compared with regards to patient's tolerability and satisfaction.

The present study has some limitations. It is a single-center study with arelatively small sample size. In addition, another limitation of the study is the sample size included in the chronic kidney disease(total of 17) and chronic liver disease(10) were small compared to elderly population(116) and diabetics(61),hence we cannot totally assessed their impact on the adequacy of bowel preparation.

Conclusion

Patients on a low residue diet for bowel preparation achieved an adequate bowel preparation that is non-inferior to patients on a clear liquid diet. Furthermore, the study showed that patients tolerability and overall satisfaction were better on the low residue diet group. Patients

in the LRD group would be more willing to repeat the same bowel regimen as compared to CLD group. However, the study also showed no statistical significance on patient's tolerability and satisfaction among diabetics, chronic kidney disease and chronic liver disease patients.

REFERENCES:

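### Efficacy in the special populations, the general objective, is settled by non-significant difference tests; no subgroup interval excludes a loss of 5 points against the 0.05 margin

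*Protocol*

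**What the plan says.** Under Objectives, the general aim is "To determine the efficacy of low residue diet for colonoscopy bowel preparation in the special populations", listed as elderly, diabetes mellitus, CKD and chronic liver disease, against clear liquids on the Boston Bowel Preparation Scale (BBPS). Under Study Design: "This study is a prospective single-blinded, randomized controlled non-inferiority trial". Under Outcomes, an adequate preparation is a BBPS of at least 6, and "A subgroup analysis to assess the efficacy of bowel preparation on special population will also be conducted".

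Under Statistical Analysis, a t-test compares means and a "chi square test will be utilized for categorical variables such as proportion of adequate bowel preparation". Then: "All significant test will be done at 5 % level". And: "A non inferiority margin of 0.05 was set". The scale of the margin is not given, and neither planned test uses it.

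Under Results, Adequacy of Bowel Preparation, the text calls the low residue diet non-inferior on mean score, reports no significant difference in adequacy (92% against 90.7%, p=0.7724), and continues: "Likewise, same conclusion can be derived from patients with Diabetes, Chronic Kidney Disease, chronic liver disease, and among elderly patients". Tables 2b to 2e give rates, means and p-values only. The Discussion names a relatively small sample as a limitation of the study. It adds that the CKD (17) and liver disease (10) groups were small compared with the elderly (116) and diabetics (61), "hence we cannot totally assessed their impact on the adequacy of bowel preparation".

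**The concern.** A non-significant difference test does not show non-inferiority. In a small subgroup, p is likely to exceed 0.05 whether or not the new diet loses more than the margin. Non-inferiority needs a confidence limit for the difference, compared with the margin, and the document does this for none of the four groups.

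This matters more than usual for a subgroup statement because these populations are the general objective. The quoted sentence is the document's answer to its main question. In two of the four groups the point estimate for adequacy lies on the unfavourable side of -5 points, so a reader relying on the sentence would take reassurance that the tables do not give.

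**Working it through.** **Inputs.** Adequate preparations (BBPS of at least 6), low residue against clear liquid, from Tables 2a to 2e: all patients 69/75 and 68/75; diabetes 27/32 and 27/29; CKD 10/11 and 6/6; liver disease 4/5 and 4/5; elderly 57/62 and 49/54. Margin 0.05 from Statistical Analysis, read here as 5 percentage points on adequacy (assumption).

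**Step 1: reproduce the stated p-values.** The chi-square multiplied by (N-1)/N gives, for diabetes, 1.1409 × 60/61 = 1.1222, p=0.2894. The same method gives 0.8199 for the elderly and 0.7724 overall. Fisher's exact test gives 1.000 for CKD and for liver disease. All match the tables. Every one tests for a difference, and none involves the margin.

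**Step 2: differences with intervals.** With d = p1 - p2 and Wilson limits (l, u) for each arm, the Newcombe limits are

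- lower = d - √[(p1 - l1)² + (u2 - p2)²]
- upper = d + √[(u1 - p1)² + (p2 - l2)²]

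Diabetes: p1 = 27/32 = 0.8438 (Wilson 0.6825 to 0.9314), p2 = 27/29 = 0.9310 (0.7804 to 0.9809), d = -0.0873.

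- lower = -0.0873 - √[(0.1613)² + (0.0499)²] = -0.256
- upper = -0.0873 + √[(0.0876)² + (0.1506)²] = +0.087

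All groups, in percentage points:

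| Group | Difference | Newcombe 95% CI | Lower limit, 90% CI |
|---|---|---|---|
| Diabetes | -8.7 | -25.6 to +8.7 | -22.7 |
| CKD | -9.1 | -37.7 to +30.7 | -32.3 |
| Chronic liver disease | 0.0 | -45.5 to +45.5 | -39.6 |
| Elderly | +1.2 | -9.6 to +12.8 | -7.7 |
| All patients | +1.3 | -8.3 to +11.0 | -6.6 |

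No lower limit is above -5 at either confidence level.

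**Step 3: does the scale of the margin matter?** If 0.05 was meant in BBPS units, the mean differences with t-based 95% intervals from the printed means and SDs are: diabetes 6.89 - 7.01 = -0.12 (-0.71 to +0.47); CKD 6.79 - 7.11 = -0.32 (-1.62 to +0.98); liver disease 7.33 - 6.47 = +0.86 (-1.29 to +3.01); elderly 7.06 - 6.90 = +0.16 (-0.25 to +0.57); all patients +0.10 (-0.26 to +0.46). No lower limit is above -0.05. These intervals are approximate: the printed summaries give p=0.687 for diabetes where Table 2b has 0.6722.

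**Step 4: how informative could the subgroups be?** Assume equal true adequacy of 0.907 in both arms (the observed clear liquid rate) and a one-sided 2.5% level. Power is then about Φ(0.05/SE - 1.96), with SE = √[0.907 × 0.093 × (1/n1 + 1/n2)]. For diabetes SE = 0.0745 and power is Φ(0.671 - 1.96) = 10%. The others are CKD 5%, liver disease 5%, elderly 15% and all patients 18%. With power this low, p above 0.05 on a difference test says almost nothing about non-inferiority.

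**The case against.** **The sentence may claim less.** It directly follows the statement that no significant difference was seen, so it can be read as saying only that. On that reading it is literally true (p=0.2894, 1.000, 1.000 and 0.8199). The Conclusion claims non-inferiority for patients overall and makes no separate efficacy claim for any special population. This stands as a point about wording. It does not rescue the answer to the general objective, because absence of a significant difference is not what a non-inferiority trial sets out to show.

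**The Discussion already adds caution.** It does so specifically for CKD and liver disease, and in general terms for the whole study. That qualifies the Results sentence. But diabetics are named as one of the larger groups by comparison, so only the general remark covers them.

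**The unfavourable estimates are fragile.** CKD turns on one failure among 11 patients and is no signal. Diabetes is 5 failures against 2: with one fewer on low residue the difference is 28/32 - 27/29 = -5.6 points, with two fewer -2.5. This stands.

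**A reader might infer that the low residue diet is worse in diabetics.** Five of its six inadequate preparations were in diabetics. By subtraction non-diabetics are 42/43 against 41/46, +8.5 points, an interaction contrast of -17.3 points (z=-1.82, p=0.07). The documents do not support that inference. The contrast was picked after seeing the data, is one of four possible, and rests on a cell with a single failure. Other methods give p from 0.049 to 0.105, and on the BBPS score the interaction p is 0.32.

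**Conclusion.** Wrong as written. The claim for the four special populations rests on difference tests alone. With the margin taken as 5 percentage points on adequacy, the 95% lower limits are -25.6 (diabetes), -37.7 (CKD), -45.5 (liver disease) and -9.6 (elderly), so non-inferiority is shown in none of them. The conclusion does not depend on the choice between 90% and 95% confidence, or on whether the margin is on adequacy or on the BBPS score.

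Two stronger readings go too far. The data do not establish inferiority in diabetes or CKD, since both intervals extend well above zero. Nor does the document claim that the diets are equivalent; it makes an ambiguous statement without the evidence that either meaning would need under its own design. The subgroup problem also sits inside a wider one, because the overall lower limit of -8.3 does not clear the margin either.

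**What to change.** In Results, Adequacy of Bowel Preparation:

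- Replace the same-conclusion sentence with the risk difference and 95% interval for each of the four groups, set against the margin, and state the scale of the margin.
- State that non-inferiority is not shown in any special population, and label the subgroup results exploratory.

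In the Discussion, extend the small-sample caveat to diabetics, noting that their estimate (27/32 against 27/29) lies beyond the margin with a wide interval and shows neither non-inferiority nor inferiority.

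If interaction tests are reported, give them for all four subgroups and call them exploratory. A pooled analysis of patients with any of the four conditions is not needed: 116 of the 150 patients are already elderly, so it would nearly repeat the overall comparison.

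The cost is a few lines of calculation on counts already in Tables 2a to 2e, and a more cautious conclusion. No new data are required.

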To determine the tolerability of low residue diet for colonoscopy bowel preparation in special populations (elderly, diabetes mellitus, chronic kidney disase, chronic liver disease) versus clear liquid diet.

Review of Related Literature

CRC screening in average-risk persons should begin at age 50, except that in African Americans, screening should begin at age 45 years. A family history of polyps need not invoke earlier onset of screening or other adjustment in screening, unless there is convincing evidence that the polyps were advanced adenomas. [8]. Given the finding that adenomatous polyps are precursors to cancer and that polyps and early cancers are usually asymptomatic, there is a

strong rationale to support screening asymptomatic individuals for early cancer detection and prevention. [3]

Colonoscopy is the current standard method for imaging the mucosa of the entire colon. Large-scale reviews have shown rates of incomplete colonoscopy, defined as the inability to achieve cecal intubation and mucosal visualization effectively, between 10% and 20%, well over targets recommended by the U.S. Multi-Society Task Force on Colorectal Cancer.[6]

The diagnostic accuracy and therapeutic safety of colonoscopy depends, in part, on the quality of the colonic cleansing or preparation. Inadequate bowel preparation can result in failed detection of prevalent neoplastic lesions and has been linked to an increased risk of procedural adverse events. [6]

In clinical practice, preparation quality should be graded after efforts to remove residual effluent and fecal debris have been completed. Validated scoring systems that have been devised to rate the quality of colonoscopy preparation in clinical trials include the Aronchick Scale, the Ottawa Bowel Preparation Scale, and the Boston Bowel Prep Score .[5]

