The proportion of patients who developed nausea and vomiting were not statistically significant between the two groups(5.35 vs 12 %,p=0.148)(Table 3a). However, the occurrence of abdominal pain/cramping/discomfort (34.7%) and bloatedness (44%) are significantly higher in clear liquid diet group compared to low residue diet group(16% and 26.7% respectively, p=0.0088 and0.0269) (Table 3a). Moreover, patients in the LRD group were less hungry before colonoscopy as compared to CLD group(4.16 vs 3.72, p=0.0027). Patient's satisfaction with the diet showed a higher proportion of patients in the LRD group rated the procedure easy(12%) and fair (78.7 %) compared to CLD group (3% and 72% respectively, p=0.0178). Likewise, in terms of willingness to repeat the procedure, patients who said yes is significantly higher for low residue diet group (93%) as compared to only 81.3% for Clear liquid diet group. On the other hand, among patients with Diabetes Mellitus, Chronic

Kidney Disease, and Chronic liver disease showed no significant difference between the two groups in terms of symptoms, hunger score, satisfaction with diet and willingness to repeat procedure.(Table 3b-3d).

Table 3e showed that among elderly patients, proportion of patients with abdominal pain(37%) was higher for Clear liquid diet group compared to LRD group (12%, p=0.0343). Finally, in terms of willingness to repeat the procedure, elderly patients who said yes is significantly higher for low residue diet group (93.5%) as compared to only (81.5%) for Clear liquid diet group.

Table 3a Patients Tolerability (Gastrointestinal Symptoms)

	Low Residue Diet (n=75)	Clear Liquid Diet (n=75)	p value
GI Symptoms			
Nausea/Vomiting,n,%	4 (5.3)	9 (12.0)	0.1481 ^{ns}
Abdominal Pain/Cramping/Discomfort, n, %	12 (16.0)	26 (34.7)	0.0088*
Bloatedness,n,%	20 (26.7)	33 (44.0)	0.0269*
Hunger Score, mean±sd	4.16 ± 0.81	3.72 ± 0.95	0.0027*
Satisfaction with Diet, n, %			
Easy	9 (12.0)	3 (4.0)	
Fair	59 (78.7)	54 (72.0)	0.0178*
Difficult	7 (9.3)	18 (24.0)	
Willingness to Repeat Procedure, n, %			
Yes	70 (93.3)	61 (81.3)	0.0277*
No	5 (6.7)	14 (18.7)	0.0277*

Table 3b Patients Tolerability (Gastrointestinal Symptoms) for DM

	Low Residue Diet (n=32)	Clear Liquid Diet (n=29)	p value
--	----------------------------	-----------------------------	---------

GI Symptoms			
Nausea/Vomiting,n,%	2 (6.2)	5 (17.2)	0.1822 ns
Abdominal Pain/Cramping/Discomfort, n, %	7 (21.9)	12 (41.4)	0.1033 ns

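### The Discussion reads non-significant tolerability results in diabetic, kidney and liver disease patients as no difference; the diabetic estimates resemble the overall ones and the result is inconclusive

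*Protocol*

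**What the plan says.** The specific objective in the protocol is: "To determine the tolerability of low residue diet for colonoscopy bowel preparation in special populations", followed by four named groups (elderly, diabetes, chronic kidney disease, chronic liver disease). Under Statistical Analysis, "t-test will be used to compare means such as BBPSscore, while chi square test will be utilized for categorical variables" and "All significant test will be done at 5 % level".

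The Discussion reports better overall tolerability and satisfaction on the low residue diet. It then turns with a 'However' to the subgroups, where "no difference was found among diabetics, chronic kidney disease and chronic liver disease patients when the two groups were compared". The Conclusion makes the same turn: "the study also showed no statistical significance on patient's tolerability and satisfaction among diabetics, chronic kidney disease and chronic liver disease patients".

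The basis is Tables 3b to 3d, which give within-subgroup p-values without confidence intervals. The limitations paragraph calls the kidney disease (17) and liver disease (10) groups small, but only with regard to adequacy of bowel preparation. It lists the 61 diabetics among the larger groups used for comparison.

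**The concern.** A significant p-value in 150 patients and a non-significant one in 61 do not show that the effect differs between the two sets. The second may be non-significant only because it has fewer patients. To say that no difference was found, the estimates would have to be near zero with intervals narrow enough to exclude a relevant effect.

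At stake is the stated answer to the specific objective for three of its four populations. A reader of the Discussion would take it that diabetics gain nothing in tolerability from the low residue diet. The tables do not show that.

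**Working it through.** **Inputs.** Overall counts are from Table 3a (75 vs 75), diabetics from Table 3b (32 vs 29), kidney disease from Table 3c (11 vs 6) and liver disease from Table 3d (5 vs 5). All differences are low residue minus clear liquid. A higher hunger score means less hungry (Table 4). Tests are taken as two-sided at 5%; the protocol does not say so, but this reproduces the printed p-values.

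**Reproducing the printed p-values.** The 2x2 results follow from the N-1 chi-square, (N-1)(ad-bc)² / [n1·n2·s·(N-s)], where s is the total number of events.
- Pain overall ("Abdominal Pain/Cramping/Discomfort, n, % 12 (16.0) 26 (34.7) 0.0088"): 149 × (12×49 - 63×26)² / (75×75×38×112) = 6.862, p = 0.0088.
- Pain in diabetics ("Abdominal Pain/Cramping/Discomfort, n, % 7 (21.9) 12 (41.4) 0.1033 ns"): 60 × (7×17 - 25×12)² / (32×29×19×42) = 2.654, p = 0.1033.
- Diabetic nausea/vomiting (0.1822), willingness (0.1229) and three-category satisfaction (0.2500, Pearson) also reproduce. Hunger gives 0.0574 against the printed 0.0578, a rounding difference.
- Diabetic bloatedness is printed as 13 with 55.2%. But 13/29 = 44.8% and 16/29 = 55.2%. The printed p of 0.0613 reproduces with 16; 13 gives 0.2785. Both readings are carried below.

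**Sizes instead of p-values.** Intervals for proportions are Newcombe 95% intervals built from the two Wilson intervals. For diabetic pain the Wilson limits are 11.0 to 38.8% and 25.5 to 59.3%. The lower limit is -19.5 - √[(21.9-11.0)² + (59.3-41.4)²] and the upper is -19.5 + √[(38.8-21.9)² + (41.4-25.5)²]. Unrounded, that is -40.4 to +3.7. For hunger the pooled SD is 0.926 and the SE 0.237, so the interval is 0.46 ± 2.00 × 0.237.

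| Item | Overall | Diabetics | 95% CI, diabetics |
|---|---|---|---|
| Abdominal pain, points | -18.7 | -19.5 | -40.4 to +3.7 |
| Nausea/vomiting, points | -6.7 | -11.0 | -28.9 to +5.9 |
| Bloatedness, 16/29 | -17.3 | -23.9 | -45.0 to +0.8 |
| Bloatedness, 13/29 | -17.3 | -13.6 | -35.7 to +10.3 |
| Willing to repeat, points | +12.0 | +14.8 | -4.3 to +33.8 |
| Diet rated difficult, points | -14.7 | -11.6 | -31.1 to +8.0 |
| Hunger score | +0.44 | +0.46 | -0.01 to +0.93 |

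Every diabetic estimate favours the low residue diet, and every interval includes both zero and the overall value.

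**What the smaller sample does.** If the overall effects held in diabetics, power at 32 vs 29 would be 39% for pain, 29% for bloatedness, 30% for willingness, 34% for a difficult rating, 49% for hunger and 16% for nausea/vomiting. Non-significance on any single item was therefore more likely than not. Conversely, the diabetic pain proportions at 75 per arm would give z = -0.195 / √(0.316 × 0.684 × 2/75) = -2.57, p = 0.010.

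**Diabetics against non-diabetics.** Subtraction leaves 43 vs 46 non-diabetics. For pain, 5/43 - 14/46 = -18.8 points. The diabetic minus non-diabetic contrast is -0.7 points (Wald 95% CI -28.9 to +27.5, p = 0.96). For willingness it is +4.2 (-18.0 to +26.4, p = 0.71). For bloatedness with 16/29 it is -10.2 (-40.9 to +20.4, p = 0.51). These contrasts give no sign of a lost benefit, but they are too wide to establish similarity.

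**The other two subgroups.** In liver disease, pain and bloatedness are each 0/5 vs 3/5, an observed difference of -60 points with Fisher p = 0.1667. The Newcombe interval, -88.2 to -3.0, just excludes zero, so at this size the answer turns on the method. In kidney disease, pain is 1/11 vs 1/6 (-7.6 points) while bloatedness is 3/11 vs 1/6 (+10.6, CI -32.8 to +42.9), against the low residue diet.

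**The case against.** Several stronger readings are tempting, and the documents do not support them.

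- *Both sections assert absence of a difference.* Only the Discussion does. The Results and the Conclusion speak of significance, and that is true of every p-value in Tables 3b to 3d. The fault in the Conclusion is the contrast it draws.
- *The specific objective got a negative answer.* It did not. In the elderly (116 of 150 patients) Table 3e reports benefit on pain (p = 0.0343), hunger (p = 0.0345) and willingness (93.5% vs 81.5%, p = 0.0475). The clear liquid pain count there, 34 of 54, does not match its 37.0%, but 20/54 does and reproduces the p-value.
- *Diabetics benefit as much as everyone else.* This is not shown. Differences between diabetics and non-diabetics of 20 to 30 points either way are not excluded, and the overall figures contain the diabetics. Reading an interaction p of 0.96 as similarity would repeat the error criticised here. The difficult rating is smaller in diabetics than overall, as is bloatedness if 13/29 is correct. Nausea/vomiting was not significant overall either (p = 0.1481).
- *The plan lacks an interaction test.* That may sit in a statistical analysis plan that is not at hand, so it is not part of this point.

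It can also be said that the authors admit small numbers. They do so in general terms and for kidney and liver disease, but the specific caveat concerns adequacy of preparation. It does not reach tolerability or the diabetics. This softens the point without removing it.

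**Conclusion.** The Discussion sentence is wrong as written. For diabetics the data are inconclusive: all estimates favour the low residue diet, broadly at the overall size, with intervals from a large benefit to little or none (pain -40.4 to +3.7 points). Liver disease (10 patients) and kidney disease (17) are too few to conclude in either direction. The Conclusion is literally correct but misleading as a contrast with the overall result. No primary result is affected.

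This rests on the printed counts, on two-sided tests at 5%, and, for the non-diabetic comparison, on subtraction from the totals. It holds under either reading of the diabetic bloatedness cell.

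**What to change.** 1. Replace the Discussion and Conclusion sentences with wording such as: *differences in diabetics, kidney disease and liver disease were not statistically significant; in diabetics the estimates were in the same direction as overall but imprecise, and kidney disease (17) and liver disease (10) are too few to conclude.* Drop the contrast with the overall benefit.
2. Give each subgroup difference in Tables 3b to 3e with its 95% CI. A diet-by-diabetes interaction estimate with its CI may be added, provided it is not read as proof of similarity.
3. Extend the small-sample limitation to tolerability and to diabetics.
4. Check the diabetic bloatedness cell against source data and reconcile count, percentage and p-value.

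The cost is a short re-analysis of data in hand and the rewording of a few sentences.
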